19.5 Quality-of-Life Analysis

UW-QoLQ v4 will be calculated at baseline and at 30 days post final treatment. The primary analysis will consist of examining the change from baseline to Day 30 using a Wilcoxon sign-rank test.

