2.6 Correlative Studies

2.6.1 QUALITY OF LIFE EVALUATION

Several clinical studies suggested that PDT and I-PDT could improve QoL in patients with locally advanced HNC. (53-56) Few studies reported that I-PDT (with Temoporfin) reduced tumor related bleeding and pain, while improving breathing, speaking, swallowing, and appearance.(50, 51, 57) The impact of Photofrin® mediated I-PDT on QoL has not been evaluated, to date.

In this protocol, participants' QoL will be evaluated with an accepted University of Washington Quality of Life Questionnaire Version 4 (UW-QoLQ v4: see **Appendix E**) (58, 59). It has been tested in several prospective studies and found to be reproducible, reliable, and valid for HNC patients: it is simple to complete, employs a simple algorithm to compute the overall score, and is easy to interpret while yielding objective results.(60) This version includes 12 individual Likert-scale items and 4 global questions. Each participant's overall score on the UW-QoLQ v4 will be calculated at baseline, at 12-16 weeks, and at 30 days post final treatment.

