11.5 Evaluations Performed at 1st Post-Operative Clinic Visit

This visit will be scheduled 1 to 4 weeks post I-PDT and will include:

- Physical examination, including vital signs (i.e., temperature, heart rate, respiratory rate, blood pressure, body weight, and pain assessment using a verbal score of 0-10)
- Hematology (i.e., CBC (with auto differential), ANC, and platelets)
- Chemistry (i.e., AST, ALT, total bilirubin, alkaline phosphatase, creatinine, potassium, glucose, and calcium)
- ECOG Performance Status
- Adverse events
- UW QoLQ v4
- Research blood draws (Optional) #

Performed as per PI discretion if later I-PDT courses are deemed necessary as per Section 10.4.

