Appendix D Schedule of Procedures and Observations if Only I-PDT Course is Necessary

Evaluation	Baseline ¹	Pre- Operative	Day of Treatment	Day 1 Post Treatment	1-week Post- treatment	Optional I-PDT Course 2 Within 2-3 Weeks of Day 0 ¹⁷	Clinic Visit ^{2,2a}	30- Day Post I- PDT ¹⁴	Optional I-PDT Treatment additional 2 or 3 At least 6 Weeks after last I-PDT Session ¹⁸	Follow- Up
Informed Consent	X									
Medical History	X								X	
Physical Exam/ Vital signs & pain assessment using a verbal score 0-10 ³	X				X		X	X	X	X
Hematology ⁴ and Chemistry ⁵	X				X		X	X	X	
Research Blood Draws ⁶			X		X		X	X	X	
Pregnancy Test (Urine)	X								X	
ECOG Performance Status	X		X		X		X	X	X	X
UW-QoLQ v. 4 ¹⁵	X				X		X	X	X	X
Standard Imaging of the head and neck with CT or MRI, for RECIST v11.1	X ⁷								X	X8
Treatment planning	X								X	
Porfimer Sodium administration and Vital Signs		X ⁹							X	
Intraoperative Ultrasound			X						X	
If possible, intraoperative CT or other clinically approved radiological imaging			X^{10}			X ¹⁰			X^{10}	
Interstitial PDT (I-PDT) 16			X^{11}			X ¹¹			X ¹¹	
Concomitant Medications	X ¹²		X							
Adverse Events ¹³			X		X		X	X		

Notes:

- * The I-PDT procedure is termed a "course".
 - 1. Performed within 8 weeks prior to porfimer sodium.
 - Performed at Day 1 of SOC therapy.
 If later 2nd and 3rd I-PDT courses are deemed necessary per the physician (see Section 10.4), please refer to Appendix D 1 for treatment, procedure, and test scheduling.
 - 3. Temperature, heart rate, respiratory rate, blood pressure, body weight and, height, Height collected at baseline only. Refer to Section 11.2.
 - 4. Hematology (i.e., CBC (with auto differential), ANC, and platelets). Refer to Section 11.2.
 - 5. Chemistry (i.e., AST, ALT, total bilirubin, alkaline phosphatase, creatinine, potassium, glucose, and calcium). Refer to Section 11.2.
 - 6. This is optional. Refer to immune markers Section 11.8 (1, 10 mL green-top tube).
 - 7. Standard tumor staging performed within 4 weeks, and at least 14 business days prior to I-PDT. If possible, the imaging will include temporary fiducial markers that will be affixed to skin. Refer to Section 11.2.
 - 8. CT scans at 10 to 12 weeks post SOC therapy and as clinically indicated following the NCNN 2018 guidelines.
 - 9. Infusion will occur 48 hours ± 8 h prior to illumination. Vitals are to be taken immediately after injection and after 15 minutes.

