 - 10. If possible, intraoperative CT (such as O arm) or another radiological imaging (e.g. C-arm) will be used to image the catheters in the tumor.
 - 11. Refer to Section 10.2.1.
 - 12. Medications ongoing within 1 week prior to porfimer sodium injection.
 - 13. AE reporting period will be for 30 days \pm 2 days post first SOC treatment.
 - 14. First SOC treatment day of I-PDT day if no therapeutic SOC treatment is administered.
 - 15. Refer to Section 11.6f patient doesn't come in or quality of life is missed, may be done via telephone.
 - 16. In the event that the tumor size is such that treating the entire tumor could cause a health risk to the patient, the current I-PDT course will be broken up into session/s. We will illuminate one part of the tumor on the day of I-PDT and another part/s of the tumor in additional I-PDT session/s within 14 days after the initial I-PDT session, at the discretion of the treating physician. If

- an I-PDT course is broken up into I-PDT sessions, the I-PDT dosage for each session will remain the same as though sessions were not broken up as dosing is dependent on number of fibers received per session. The patient will not need to receive additional doses of porfimer sodium if having additional I-PDT sessions within 14 days after the previous I-PDT session as porfimer sodium is expected to be in the tumor for at least 30 days.
- 17. Another (one or two, total of three) laser light treatment(s) only (no additional drug) within 2-3 weeks of the initial administration of Photofrin.
- 18. Patient may receive a second complete I-PDT treatment that will include drug and light administration. It will be at the discretion of the treating physician to administer this additional treatment. Another CT (charged to the study if it is not SoC) will be done, and all tests will be conducted before and after additional treatment, according to the same schedule parameters as the initial treatment.

Appendix D 1 Schedule of Procedures and Observations (Only for Dose Escalation later I-PDT Sessions if Deemed Necessary by Physician)**

Evaluation	Repeat of Initial Tests and Procedures ^A	Pre- Operative	Day of Treatment	1-week Post- treatment	Clinic Visit	Post- Treatment	Follow- Up
Physical Exam/ Vital signs ^B & pain assessment using a verbal score 0-10	X			X	X	X	X
Hematology ^C and Chemistry ^D	X			X	X	X	
Research Blood Draws ^E			X	X	X	X	X
Pregnancy Test (Urine)	X						
ECOG Performance Status	X		X	X	X	X	X
UW-QoLQ v. 4 ^p	X			X	X	X	X

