 - F. If required per physician's discretion, standard tumor staging performed within 4 weeks, and at least 14 business days prior to following I-PDT. If possible, the imaging will include temporary fiducial markers that will be affixed to skin. Refer to Section 11.2.
 - G. CT scans at 10 to 12 weeks post I-PDT and as clinically indicated following the NCNN 2018 guidelines.
 - H. If tumor results determine porfimer sodium infusion is needed for later 2nd and 3rd I-PDT sessions, infusion will occur 48 hours ±8 h prior to illumination. Vitals are to be taken immediately after injection and after 15 minutes.
 - I. If possible, intraoperative CT (such as O arm) or another radiological imaging (e.g. C-arm) will be used to image the catheters in the tumor.
 - J. Refer to Section 10.2.1.
 - K. Medications ongoing within 1 week prior to illumination.
 - L. Refer to Section 10.2.1.
 - Li. The later 2nd and 3rd I-PDT study treatments total as per the physician's discretion are at least 30 days apart from each other (see Section 10.4). For additional I-PDT treatments that are 30 days from the previous that require an additional dosage of porfimer sodium the porfimer sodium (2mg/kg) is administered 48 hours prior to illumination.
 - M. AE reporting period will be for 30 days \pm 2 days post first SOC treatment.
 - Oi. Since there may be up to three I-PDT courses, at least 30 days apart (see Section 10.4), per the physician's discretion, adverse events review of previous study treatments are reviewed prior of the next additional I-PDT.
 - N. In Phase 1, patients are off treatment/on follow up as clinically indicated 30 days after the last I-PDT.
 - O. Refer to Section 11.6 if patient doesn't come in or quality of life is missed, may be done via telephone.

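### The documents contradict each other on when the Day 30 quality-of-life score is taken, and under Appendix D note 14 the single test would pool scores dated from I-PDT with scores dated from the start of standard-of-care therapy

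*Combined protocol and SAP*

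**What the plan says.** Section 2.6.1 gives the reason for collecting the questionnaire: "The impact of Photofrin® mediated I-PDT on QoL has not been evaluated, to date". It says that the overall score "will be calculated at baseline, at 12-16 weeks, and at 30 days post final treatment".

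Section 19.5 keeps two of those times: "UW-QoLQ v4 will be calculated at baseline and at 30 days post final treatment". The analysis is one paired test: "The primary analysis will consist of examining the change from baseline to Day 30 using a Wilcoxon sign-rank test". Neither section says whether the final treatment is I-PDT or SOC. Section 19.5 gives no rule for participants who have started SOC.

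In Appendix D the UW-QoLQ is marked at several visits, but only one column is a 30-day column. Its header dates it from I-PDT. Note 14 on that header reads: "First SOC treatment day of I-PDT day if no therapeutic SOC treatment is administered". The word *of* appears to stand for *or*, because Section 19.3 sets out the same two-way clock for safety. The Clinic Visit column, which comes before it, carries note 2: "Performed at Day 1 of SOC therapy".

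Section 11.5 describes the first post-operative clinic visit, which also collects the questionnaire: "This visit will be scheduled 1 to 4 weeks post I-PDT and will include".

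Other parts count 30 days from the last I-PDT. Sections 8.1 and 10.3 do so for adverse events and dose-limiting toxicity, and Appendix D 1 note N says: "In Phase 1, patients are off treatment/on follow up as clinically indicated 30 days after the last I-PDT". Appendix D 1, for participants with later courses, marks the UW-QoLQ in a Post-Treatment column that has no counterpart to note 14.

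**The concern.** A paired test of change from baseline needs the second score to mean the same thing in every participant. Here two people could follow the documents in good faith and collect different data: one dates the questionnaire by the column header, the other by its footnote.

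Under the footnote, a participant who starts SOC is scored after 30 days of it. The questionnaire in Appendix E asks about the past seven days, so all of that recall falls after SOC began. A participant without SOC is scored 30 days after I-PDT. Section 19.5 analyses both as Day 30.

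This is not remote. Section 2.5 accepts that patients with locally advanced disease need systemic therapy, and both schedules tie the Clinic Visit to the start of SOC. The trial has no control arm and at most 12 participants, so nothing in the analysis could separate a change due to SOC from one due to I-PDT.

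**Working it through.** **Step 1. The rules for the 30-day clock, side by side**

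| Place | 30 days counted from |
|---|---|
| 19.5 and 2.6.1 (quality of life) | final treatment, not defined |
| Appendix D, header of the 30-day column | I-PDT |
| Appendix D note 14, on that header | first SOC day; I-PDT day if no SOC |
| 19.3 (safety analysis) | first SOC day; last I-PDT day if no SOC |
| Appendix D note 13 and Appendix D 1 note M (adverse events) | first SOC treatment |
| 8.1 and 10.3 (adverse events, dose-limiting toxicity) | final I-PDT |
| Appendix D 1 note N (end of treatment) | last I-PDT |

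Only the first three rows bear on the questionnaire directly, and they do not agree. The rest show that both clocks are in use elsewhere, so note 14 cannot be set aside as an isolated slip.

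**Step 2. What note 14 does to the date of the score**

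Let *s* be the day SOC starts, counted from I-PDT. Under note 14 the score falls on day *s* + 30, or on day 30 if no SOC is given. The documents do not give *s*. Assume that SOC Day 1 (Appendix D note 2) is the Section 11.5 visit at 1 to 4 weeks, so *s* is 7 to 28:

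- no SOC: day 30
- *s* = 7: 7 + 30 = day 37
- *s* = 28: 28 + 30 = day 58

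Scores pooled under one label would then differ by 7 to 28 days in time since I-PDT (7/30 = 23% to 28/30 = 93% of the nominal interval). A later SOC start widens the gap: *s* = 30 gives day 60.

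**Step 3. What a single I-PDT clock does**

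Every score falls on day 30. SOC exposure by then is 30 − *s* days: 23 days if *s* = 7, 2 days if *s* = 28, and none if SOC starts on day 30 or later. The spread in dates disappears, but SOC exposure may not.

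**Step 4. Illustration of the effect on the test**

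Section 19.5 states no significance level, effect size or standard deviation, so there is no planned figure to reproduce. The illustration assumes 12 participants (the maximum in Section 19.1), normal changes with SD 1, no I-PDT effect, an exact two-sided signed-rank test at 0.05, and 4,000 runs. SOC starters are shifted downward by the amount shown.

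| SOC starters of 12 | Rejects, shift 0.5 SD | Rejects, shift 1.0 SD |
|---|---|---|
| 0 | 0.050 | 0.044 |
| 3 | 0.052 | 0.080 |
| 6 | 0.097 | 0.231 |
| 9 | 0.187 | 0.525 |
| 12 | 0.324 | 0.844 |

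The two values in the first row differ only by simulation error. The mean change is displaced by the SOC share times the shift, for example 9/12 × 0.5 = 0.375 SD. An upward shift would give the same rates with the opposite sign. The SOC share and the shift are both assumed, so the table shows how the test would respond and is not a forecast for this trial.

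**The case against.** A reader might infer that the plan has settled on the SOC clock and will report a month of SOC toxicity as an I-PDT effect. The documents do not support that. Section 19.5 does not mention SOC, the column header says I-PDT, note 14 is garbled, and Sections 8.1 and 10.3 and note N use the last I-PDT. Section 19.5 tests a change from baseline and does not attribute it to I-PDT; that purpose comes from Section 2.6.1. SOC could also improve scores. This objection stands: the fault is a contradiction, not a settled wrong rule.

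The day 37 to 58 range is also not a timing the documents state. Section 11.5 never mentions SOC, and equating its visit with SOC Day 1 is a reading. Nor is the 30-day column in Appendix D the only source of a post-treatment score, since Appendix D 1 has its own column for later courses. Both points stand.

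Finally, an uncontrolled before-and-after comparison in advancing cancer cannot isolate I-PDT under any clock, and quality of life is neither a listed objective nor a listed endpoint. That is true and limits the weight of the point. It does not excuse leaving open the date of the only planned quality-of-life comparison, because a common date is the least that a paired test needs.

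**Conclusion.** The point holds as a contradiction that needs to be reconciled. The treatment that starts the Day 30 clock is undefined in Sections 19.5 and 2.6.1, and Appendix D answers it in two incompatible ways within one column. If note 14 is followed, the signed-rank test pools scores taken at different times after I-PDT, some of them after a month of SOC, and the result cannot be read as the quality-of-life impact of I-PDT.

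The gap is 7 to 28 days if SOC starts at the 1-to-4-week visit, which is an assumption. The number of participants who will start SOC, the effect of SOC on the score, and hence the size and direction of any bias are unknown. The rejection rates above are illustrative only. The measure is correlative, so neither dose finding nor the recommended light dose depends on it.

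**What to change.** 1. In Sections 19.5 and 2.6.1, in Appendix D and in the Post-Treatment column of Appendix D 1, define the quality-of-life Day 30 as 30 days after the final I-PDT for every participant, whether or not SOC has started. State that note 14 does not set the questionnaire date.
2. Record the SOC start date. Show the Day 30 change descriptively for participants who had and had not started SOC by then. This is needed because the common clock alone can leave up to 23 days of SOC exposure, on the timing assumed above.
3. As a labelled sensitivity analysis, for participants who started SOC before Day 30, use the Clinic Visit questionnaire already scheduled for SOC Day 1, completed before the first SOC dose, as their post-I-PDT value.

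The cost is a wording change, one recorded date, one descriptive split and one extra run of a planned test. No new questionnaire or visit is needed, since Appendix D note 15 already allows telephone completion. There are two drawbacks. The pre-SOC score is earlier than day 30, so the third item mixes times and can only be supportive. With at most 12 participants, the subgroups will be very small.

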19.6 Adverse Events

The frequency of toxicities will be tabulated by grade across all dose levels and cycles. All subjects who receive any study treatment will be considered evaluable for toxicity.

19.7 Interim Analysis and Criteria for Early Termination of the Study

A formal stopping rule for safety is given in Section 19.1. In addition, the Phase 1 study will be monitored and discussed by Roswell Park's Early Phase Clinical Trials Committee, which meets on a regular basis per the Roswell Park Data Safety Monitoring Plan. Drug safety will be monitored and evaluated continuously throughout the study including 30-day safety follow-up period by obtaining, reviewing and analyzing data on AEs, changes in laboratory values, vital signs, electrocardiograms (ECGs), and physical examination findings. Potential early termination decisions are an inherent part of the Phase 1 study monitoring.

Specific attention will be paid to incidents of:

- 1. Life threatening hemorrhaging
- 2. Airway compromise leading to emergency intubation or tracheostomy

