4.0 Local and Study-Wide Number of Subjects

In the Phase 1 study, a maximum of 12 (four cohorts of 3) evaluable participants at Roswell Park, will be enrolled. The number of subjects required is a function of the unknown dose-toxicity.

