10.3 Definition of Dose-Limiting Toxicity

Dose Limiting Toxicities will include:

Any adverse events (AEs) that are \geq grade 4 that are possibly, probably, or definitely related to the I-PDT, by recording the occurrence of AE during the first 30 days post final I-PDT treatment using the revised the National Cancer Institute (NCI) Common Terminology Criteria for Adverse Events version 5.0 (CTCAE v5.0). Dose Limiting Toxicities will be evaluated for 30 days post final I-PDT day.

If participants experience DLTs, further I-PDT sessions will be held until DLT resolution as well as after porfimer sodium clearance.

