10.4 Dose Escalation/Finding Schema

The FDA approved porfimer sodium dose (2 mg/kg) will not change. We will aim to deliver light fluence rate of ≥ 8.6 mW/cm² and fluence of ≥ 45 J/cm² to 100% of the CTV (dose level 1), as much as possible. Dose level -1 will ≥ 5.0 mW/cm² and fluence of ≥ 45 J/cm² to 100% of the CTV.

Table 2. The study plan for finding optimal fluence rate in I-PDT with Photofrin in patients with LAHNC.			
Dose Level Number of patients with DLT at a given dose level		Decision rules	
Dose Level 1 (Starting): The maximum fluence rate, scaled for	0 out of 3	Enter 3 patients at Dose Level 1 : The laser fluence rate and fluence, scaled for human, which induced maximum photoreaction in the animal models	
human, which induced effective	1 out of 3	Enter 3 more patients at this Dose Level .	

photoreaction in the animal models.	≥2	Enter 3 patients at Dose Level -1 : The laser fluence rate and fluence, scaled for human, which induced minimal toxicity in the animal models.
	≤ 1 out of 6	This is generally the recommended Phase II dose rate/dose. At least 6 patients must be entered at the recommended Phase II dose.

In participants where their tumors may require more than one course of I-PDT for complete effective illumination of the CTV, up to three sessions of I-PDT may be performed, at the discretion of the treating physician. The FDA approves to administer up to three courses of PDT with Photofrin® each separated by at least 30 days in the treatment of esophageal and endobronchial cancer (http://www.photofrin.com/wp-content/uploads/2013/02/prescribing-info.pdf.). Therefore, treatment sessions in this study will be conducted at least 30-days apart. The porfimer sodium dose (2 mg/kg) will remain the same.

See Appendix D 1 for the Dose Escalation Schedule of Events. The date of the last I-PDT course will be used to determine the scheduling of the follow up SoC related to this study.

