19.1 Sample Size Determination

The maximum sample size is 12 patients. The actual sample size depends on the unknown dose-toxicity profile of the treatment, see section 10.14 for the dose escalation scheme.

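### Section 19.7 cites a formal safety stopping rule that Section 19.1 does not contain; Table 2 is silent on two or more DLTs at Dose Level -1, and the 19.3 safety window runs from the wrong date

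*Combined protocol and SAP*

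**What the plan says.** Section 19.7 (Interim Analysis and Criteria for Early Termination) opens with "A formal stopping rule for safety is given in Section 19.1". It then adds early-phase committee review and two events for special attention: life-threatening bleeding, and airway compromise needing emergency intubation or tracheostomy.

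Section 19.1 (Sample Size Determination) gives the maximum of 12 and then says "see section 10.14 for the dose escalation scheme". Section 10 ends at 10.5; the scheme is in 10.4.

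Table 2 in 10.4 has a column headed "Number of patients with DLT at a given dose level". Its first column names Dose Level 1 as the starting level, and its rows are 0 of 3, 1 of 3, two or more, and at most 1 of 6. Two or more DLTs sends the next 3 patients to Dose Level -1. The last row adds "At least 6 patients must be entered at the recommended Phase II dose". Section 4.0 sets "a maximum of 12 (four cohorts of 3) evaluable participants".

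Section 10.3 defines a DLT as an adverse event of grade 4 or higher "that are possibly, probably, or definitely related to the I-PDT", and says "Dose Limiting Toxicities will be evaluated for 30 days post final I-PDT day". Section 8.1 uses the same anchor for the primary endpoint.

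Section 19.3 (Safety Analysis) uses a different clock: 30 days from the first SOC treatment, or from the last I-PDT if no therapeutic SOC is given. It says that sequential boundaries will monitor the SAE rate, citing reference 64, and that accrual halts if SAEs are excessive. Appendix D notes 13 and 14 and the Appendix D 1 note lettered M also use the first SOC treatment.

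**The concern.** Safety is the primary objective (1.1, 19.0), and 19.7 presents committee oversight as an addition to a formal rule. If that rule is missing from the cited place and incomplete in the places that could replace it, the committees have no written count for the case that matters most: toxicity at the lowest available level. Accrual there could continue, or stop, on judgement alone.

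The window is a separate fault in the same safety plan. Events after I-PDT but before SOC are the ones most directly informative about I-PDT, and the literal 19.3 window leaves them out of the safety analysis and of the SAE count that is meant to halt accrual.

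**Working it through.** **Cap.** Two levels × 6 patients = 4 cohorts × 3 = 12, which reproduces the plan's maximum. No stopping-rule figure is stated, so none can be reproduced.

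**Actions by level in Table 2.**

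| DLTs | Dose Level 1 | Dose Level -1 |
|---|---|---|
| 0 or 1 of 3 | 3 more at level 1 | no row |
| at most 1 of 6 | recommended dose | no row of its own; the criterion is worded generally |
| 2 or more | go to level -1 | no row |

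**How often the gap is reached.** The documents give no DLT rate, so a range is assumed. Also assumed are decisions after each cohort of 3 and expansion to 6 after 0 or 1 of 3 at either level. For a true rate p at one level:

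- a = P(Bin(3, p) ≥ 2): the level fails in its first cohort.
- f = P(Bin(6, p) ≥ 2): the level fails at 3 or at 6.
- b = f − a: the level fails only at 6.
- Both levels fail: f₁ × f₂.
- Both fail with places left: a₁a₂ + a₁b₂ + b₁a₂. This leaves 6 places if both fail at 3, and 3 if one fails at 3 and the other at 6. If both fail at 6, none remain.

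Example at 20%: a = 0.104, f = 0.345, b = 0.241. Both fail: 0.345² = 0.119. Places left: 0.104² + 2 × 0.104 × 0.241 = 0.061.

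| Rate at level 1 / level -1 | Both fail | Both fail, places left |
|---|---|---|
| 10% / 10% | 1.3% | 0.6% |
| 15% / 15% | 5.0% | 2.3% |
| 20% / 20% | 12% | 6% |
| 30% / 30% | 34% | 20% |
| 40% / 40% | 59% | 42% |
| 20% / 10% | 3.9% | 1.9% |
| 30% / 20% | 20% | 11% |

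A DLT must be grade 4 or higher and at least possibly related, while the ungraded risks listed in 13.0 peak at 15%. Rates of 30-40% are therefore high-end assumptions.

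**Windows.** Let SOC start d days after the final I-PDT. The 8.1 and 10.3 window covers days 0 to 30; the 19.3 window covers days d to d + 30. They share 30 − d days, and nothing once d exceeds 30. Days 0 to d fall outside 19.3. Section 17.4.1 collects new SAEs from consent until 30 days after the last intervention or the start of a new treatment, whichever is first, with related SAEs still reportable after the 30-day follow-up. If SOC counts as a new treatment, routine collection closes just as the 19.3 window opens.

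**SAE boundary.** Section 19.3 gives no acceptable rate, crossing probability or counts. Under an exact continuous (Pocock-type) boundary over 12 patients with crossing probability at most 5%, assumed acceptable rates of 10%, 20%, 30% and 40% give a halt at patient 12 with 4, 6, 8 or 9 SAE patients. At most 10% gives 4, 6, 7 or 9. The text does not determine which applies.

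**The case against.** The strongest reply is that any reader of a 3+3 scheme stops after two DLTs at the lowest level, and that oversight exists: committee review (19.7), DSMC recommendations (20.0) and institutional termination (18.4). Section 19.3 commits to halting for SAEs at any level, and a related grade 4 event will usually be serious. This stands as mitigation. It rules out the inference that the trial has no safety stop at all; the rule is incomplete, unquantified and mis-cited. But none of these protections supplies a DLT count that stops accrual at Dose Level -1.

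A reader might infer from the column heading that the two-or-more row carries down, so that Table 2 directs 3 more patients to a failed Dose Level -1. It does not. The rows belong to Dose Level 1. Carried down, the 0-of-3 row, "Enter 3 patients at Dose Level 1", would send a clean cohort at -1 back to the level that had just failed. The table is silent; it does not direct re-entry.

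A reader might also infer that 3 or 6 patients would be exposed needlessly. That is an upper bound. The cap is a maximum, and no text says that open places must be filled.

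Nor does inpatient PDT (24.0) by itself make planned admissions SAEs: 17.4 requires an adverse event that results in hospitalization.

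**Conclusion.** The point holds and should be fixed. The rule cited in 19.7 is not in 19.1, Table 2 gives no action for two or more DLTs at Dose Level -1, and the 19.3 window contradicts 8.1 and 10.3.

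The Table 2 gap is modest. At assumed equal DLT rates of 10-20%, both levels fail in 1-12% of trials, and in 0.6-6% the missing stop could matter because places remain; at 30% the figures are 34% and 20%. If -1 is the safer level, they are lower. The recommended-dose conclusion would not change: taking the at-most-1-of-6 criterion as general, a failed -1 could not be recommended. Up to 3 or 6 patients would be spared only if accrual would otherwise have continued.

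The window fault rests on the text alone and needs no assumed rate. It concerns what 19.3 counts. Section 17.4.1 still requires SAEs between I-PDT and SOC to be reported, so it should not be read as a failure to collect them. The missing SAE counts and the wrong cross-references are, on their own, missing detail and clerical error.

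**What to change.** 1. Add Dose Level -1 rows to Table 2: 0 or 1 of 3, enter 3 more at -1; at most 1 of 6, recommended dose; two or more DLTs at any point, stop accrual with no recommended dose.
2. Run the 19.3 window from first study treatment through 30 days after the final I-PDT, stating that it covers every course. This matters because 10.4 allows up to three, at least 30 days apart, and a window opening only at the final I-PDT would miss events after earlier ones. Change Appendix D notes 13 and 14 and Appendix D 1 note M to match.
3. Point 19.7 to 10.4 and 19.3, and point 19.1 to 10.4.

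Secondarily, print the 19.3 boundary as event counts, with the sponsor's acceptable rate, crossing probability and attribution rule. State whether it counts by dose level or pooled, and how it interacts with de-escalation. For illustration, a pooled boundary at an acceptable rate of 20% and crossing probability at most 5% halts at 3 SAE patients among the first 3. If those events were DLTs, Table 2 would instead send the next 3 patients to Dose Level -1.

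Items 1 to 3 cost only wording in 10.4, 19.1, 19.3, 19.7 and the two schedules, and add no patients. The secondary item needs sponsor decisions on rate, crossing probability, attribution and pooling.
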